This randomized controlled trial (RCT) is based on the hypothesis that physical activity improves cognitive functioning. The aim is to test the efficacy of physical activities for OST-patients, measured in terms of improvement of physical fitness, cognitive functioning, drug dependence and experience of improved quality of life.

The objectives of this study are to investigate (1) how physical activity affects the patient's physical fitness, and (2) how physical activity influences psychosocial and cognitive functioning.

Physical activity has a good cost-benefit ratio, is relatively easy to implement, and can help patients on several levels: They can improve their physical and mental health, as well as increase their quality of life. Many OST-patients have reduced physical health. Exercise can support them in terms of comorbidity, and to get in better physical shape. Decent physical health can prevent and improve diseases and disorders, and better shape can strengthen self-esteem and a sense of achievement. This, in turn, can increase the likelihood of successful treatment. Additionally, exercise can contribute to a change of settings, i.e. OST-patients change from a substance use/treatment environment to a sports milieu. They can become part of a community that is interested in a healthy lifestyle. Their attention can change from illness to health, both in terms of body and mind.

Another goal is for physical activity to be established as a permanent offer for all OST-patients, and that the research can strengthen and defend the existence of already established initiatives such as *Arna Aktiv* (Arna active) and *Fritid med bistand* (leisure assistance program). The use of training contacts can contribute to a lower threshold for participation in sports and aftercare services. This contact will also provide a sense of security to a vulnerable and exposed group.

The PhD candidate is responsible for the execution of the RCT. They will recruit patients, carry out the data collection and analyze the results.

4. Feasibility

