4.1 Study design, choice of methodology and analysis

The number of participants is estimated at 60, recruited from OST-facilities within the Helse Bergen area. To be eligible for admission to the study, participants must (a) sign a written informed consent to participate in the project, (b) be participating in the LAR²-program, (c) be on a steady fixed dose of medication and (d) be at least 18 years of age. Exclusion criteria are pregnancy in women and having joined the LAR-program for less than three months ago. Enrolment in the project will be a consecutive process until the required number of participants is recruited. Participants will be randomly selected for the intervention group or the control group. The intervention group will be given their training contacts (Skrede, Munkvold, Watne, & Martinsen, 2006). Together they will decide on a training schedule that suits the individual with regard to frequency, amount and type of training. Central aspects are user involvement and individual adaptation. All training programs have in common that they include endurance and strength exercises and that the intensity will increase during the intervention period. A representative group, who will not be given an intervention, serves as the control group. The project organizer/PhD candidate will be in touch frequently with members of the control group in order to keep them motivated to stay on the waiting list and to offer social contact. The participants will also answer a Likert scale question that documents the amount of physical activity and drug use the past fortnight.

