In this study, participants with particular characteristics that predispose them to have certain outcomes will be selected. This does not apply to the eventual participants since they will be randomly selected into the experimental and the control group. However, it does apply to the general selection of participants, the recruitment. Population choice is restricted since only patients interested in physical activity will participate (recruitment bias). Participation is voluntary to ensure that patients complete the trial period and thus minimize the dropout rate. OST-patients not interested in physical activity are not excluded from the project, but will most likely lack the motivation for activity/training over a longer period of time, and will therefore not wish to participate. Hence, it is difficult to obtain a representative sample of the OST-population, which will result in poor generalizability of the results. The degree to which the results can be generalized is limited; the study's results are not applicable to other groups. The selection criteria allow only a generalization to groups with similar presuppositions. Motivation is perhaps the main factor in this respect. It supposedly confines the treatment to groups that are motivated. Forcing SUD-patients to be physically active will most likely result in a different outcome. That means that the findings might only apply to patients who want to be physically active. The sample is, in this regard, not representative of the whole population. This is something one has to keep in mind when implementing training into addiction treatment. It might only be useful for patients with certain presuppositions, not for the whole population of OST-patients.

Nevertheless, the reason for only working with patients who communicate an interest in study participation is that people not interested in exercise probably will show low adherence, and adherence is a prerequisite for treatment success. Physical training is not a "quick fix" for everybody; motivation to complete the training is decisive (Donaghy, 1997).

² LAR = *Legemiddelassistert rehabilitering* (Opioid substitution therapy)

The number of patients interested in exercise might not be so low after all: SUD patients usually express an interest in physical activity (Powers, Woody, & Sachs, 1999), so the offer of such treatment might be welcomed.

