Testing consists of two parts: A battery of cognitive and psychosocial assessments and an assessment of physical variables. The following paragraphs demonstrate the different methods and measures that will be used in the project.

An endurance test (ventilatory threshold/ VO_{2max}) will be given. There will be strength and agility exercises as used by the KAN study (The Norwegian Directorate of Health/Norwegian School of Sport Science)³: Push-ups and the Stork Balance Test. The push-up test is a maximal test where the participants perform a maximum number of correct push-ups. The balance test is a timed test where the goal is to keep one's balance as long as possible.

Ventilatory threshold test: This test is performed on a treadmill. The participant starts without warming up on the starting load after being explained the test procedure and how to record the rating of perceived exertion (RPE) (Borg, 1970): stage duration 1 min, start load 6 km/h, gradient angle 5 %. Increase in load: 1 km/h. Oxygen uptake and heart rate are continuously measured during the test at 10 s intervals with the help of a metabolic cart, MetaMax II (Cortex Biophysik GmbH, Germany) and a Polar heart rate monitor (Polar OY, Kempele, Finland).

Strength and agility tests: Push-ups with a straight body, from chest touching the floor to fully extended arms. The Stork Balance Test involves keeping one's balance on one leg for as long as possible; once with open and once with closed eyes. These tests are chosen because of ease of administration and the availability of such data for comparison.

Test equipment: Treadmill: Sole Incline TT8
 Metabolic analyzer: Cortex MetaMax II
 Software: Cortex MetaSoft 1.11.05
 RPE: Borg RPE scale (1970)

The change in endurance fitness will be evaluated on the basis of the VO_{2max} , where workload at threshold point will quantify the endurance capacity. The change in the number of push-ups and the balancing time will be used for the strength/agility measures.

The study will investigate changes in satisfaction with life, executive functions and psychological distress over a period of 12 months. A battery of cognitive and psychosocial assessments will be used (a modified version of the one used in the "Executive functions in patients with substance use disorders: effects on the course of treatment" project (Stayer study)⁴):

- National Quality Register⁵
- AUDIT-E - Alcohol Use Disorders Identification Test (Extended)

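### The treadmill test has no stage below 6 km/h at 5% slope, so workload at the ventilatory threshold has a built-in floor of unknown extent

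*Protocol*

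**What the plan says.** Protocol section 4.1 describes one treadmill test for everyone. On the start it says "The participant starts without warming up on the starting load", and the schedule is "stage duration 1 min, start load 6 km/h, gradient angle 5 %. Increase in load: 1 km/h". Gas exchange and heart rate are read every 10 seconds.

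The endurance outcome has two parts, given in one sentence. It opens "The change in endurance fitness will be evaluated on the basis of the" VO2max and continues "where workload at threshold point will quantify the endurance capacity".

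On who will be tested, section 3 says "Many OST-patients have reduced physical health". Section 4.1 sets no fitness requirement for entry: "Exclusion criteria are pregnancy in women and having joined the LAR-program for less than three months ago". It also says that participants will be self-selected for interest in exercise. Retests must follow the same procedure as the baseline test.

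The protocol gives no expected VO2max or threshold for this population, and no reason for the chosen start load.

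**The concern.** A threshold workload can be read only if the test presents loads on both sides of the threshold. Here the lowest load presented is already a brisk uphill walk, and it is the first minute of the test. If a participant's threshold lies at or below that load, the recorded value can only be 6 km/h or missing. If training raises the threshold but leaves it at or below the first stage, the recorded change is zero or missing.

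Physical fitness is the first of the trial's two objectives. If many participants sit at the floor, the difference between arms in threshold workload is compressed. Because retests must be identical, the same floor applies at every later visit. An analysis plan cannot repair this afterwards, because the lower loads were never presented.

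**Working it through.** **1. The floor, from the protocol alone.** The loads presented are 6, 7, 8, ... km/h at 5% slope, one minute each. The threshold workload can therefore take the values 6, 7, 8, ... or none. No outside figure is needed for this step. There is also no plan figure to reproduce, since the start load is stated without a derivation.

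**2. How many could be affected.** This step rests on assumptions that are not in the documents:
- oxygen cost of walking (ml/kg/min) = 0.1·S + 1.8·S·G + 3.5, with S in m/min and G the slope
- threshold at 60-80% of VO2max
- VO2max normally distributed with SD 8 and mean 30 to 45 ml/kg/min

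First-stage cost: S = 6000/60 = 100 and G = 0.05, so 10 + 9 + 3.5 = 22.5.

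VO2max at which the threshold just equals the first stage: 22.5/0.8 = 28.1; 22.5/0.7 = 32.1; 22.5/0.6 = 37.5.

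Share at or below the first stage = Φ((22.5/fraction − mean)/8). For mean 35 and fraction 0.6, this is Φ((37.5 − 35)/8) = Φ(0.31) = 0.62.

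| Mean VO2max | Threshold at 80% | at 70% | at 60% |
|---|---|---|---|
| 30 | 41% | 61% | 83% |
| 35 | 20% | 36% | 62% |
| 40 | 7% | 16% | 38% |
| 45 | 2% | 5% | 17% |

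The assumed cost matters as well. At 20 ml/kg/min the ranges for means 30, 35, 40 and 45 are 27-66%, 11-42%, 3-20% and 1-7%. At 28 (a running equation, 0.2·S + 0.9·S·G + 3.5 = 20 + 4.5 + 3.5) they are 73-98%, 50-93%, 27-80% and 11-58%. All these shares are approximate: the cost is a steady-state value, and oxygen uptake lags in a one-minute stage begun from rest.

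**3. What a floor does to the arm comparison.** Section 4.1 supplies 30 per group, a significance level of 0.05 and 0.5 as the clinically relevant effect size. Take a true standardised difference of 0.5 and set every value below the floor to the floor. With floor c = Φ⁻¹(share of controls at the floor), the control mean is c·Φ(c) + φ(c). The intervention mean is 0.5 + (c − 0.5)·Φ(c − 0.5) + φ(c − 0.5).

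For 50% of controls at the floor, c = 0. The control mean is 0.399 and the intervention mean is 0.5 − 0.5 × 0.309 + 0.352 = 0.698. The difference is 0.299, and 0.299/0.5 = 60%.

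Simulation of two-sided t-tests, 30 per arm:

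| Controls at floor | Raw difference kept | Standardised difference | Power |
|---|---|---|---|
| none | 100% | 0.50 | 0.48 |
| 10% | 94% | 0.50 | 0.47 |
| 25% | 82% | 0.49 | 0.45 |
| 50% | 60% | 0.45 | 0.40 |
| 75% | 34% | 0.38 | 0.30 |

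Power falls less than the raw difference because the floor also shrinks the spread.

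**The case against.** The strongest reply is that nothing in the protocol shows the floor will matter. The documents give no fitness figure, and the computed shares run from 2% to 83% at walking cost alone. Reduced physical health is a qualitative remark about substitution-therapy patients in general, whereas the sample is self-selected for interest in exercise. With 10% or 25% of controls at the floor, power moves only from 0.48 to 0.47 or 0.45. All of this stands. A reader might infer that most participants start above their threshold; the documents do not establish that.

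A second reply is that VO2max is also named as the basis for judging change, and a high start load does not left-censor it in the same way. This stands too. A reader might infer that the endurance outcome as a whole has a floor, but only threshold workload does.

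Third, how to score an undetected threshold is commonly left to the analysis plan, so its absence from the protocol is not a fault. That is right, but it does not dispose of the point. The start load is a data-collection choice fixed in the protocol, and no scoring rule recovers information the test did not collect.

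**Conclusion.** The point holds for workload at the ventilatory threshold: the protocol's own test specification puts a floor under that measure. Its extent is unknown. Under the stated assumptions it runs from negligible in a fit sample (2-17% at a mean VO2max of 45) to possibly a majority in an unfit one (41-83% at 30). The effect on the comparison is small up to about a quarter of controls at the floor and substantial from about half.

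Two further inferences are tempting but unsupported. One is that the floor falls where the largest change is expected; no passage says that the least fit should gain most. The other is that a cold start contradicts the gradual build-up of training intensity; that instruction concerns the 12-week programme, not the test.

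This is a cheap improvement to a measure serving the first objective. It does not show that the endurance result would be invalid.

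**What to change.** Before testing starts, amend the treadmill description in section 4.1 to add lower-speed stages ahead of the 6 km/h stage, identical for every participant and every visit. This lets low thresholds be recorded and leaves the present stages in place above them. Keep VO2max from the same test as the measure that the floor does not censor in the same way.

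The cost is a changed treadmill program and a few more minutes per test, with the same equipment and staff. The downside is less direct comparability with earlier data collected from the present start load. Timing matters: retests must match baseline, and a change made after the first baseline tests would leave a 60-person trial with two versions of the test.

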Data generated in this project will mostly be on interval or ratio level (whether the rating of perceived exertion is ordinal or interval data will not be discussed here). To express group results, the mean will serve as a measure of the central tendency, with the standard deviation expressing the spread of results within the group. If useful, the standard error of the mean (SEM) will be used to express

⁶ Based on the WHO's recommended levels of physical activity for adults aged 18 - 64 years (http://www.who.int/dietphysicalactivity/factsheet_adults/en/)

the accuracy of the mean value. If results are highly skewed (skewness > 1.5), a log transformation and geometric mean will be used together with a 95% confidence interval to express central and spread tendencies. To compare results over time, an ANOVA/t-test of repeated measures will be performed with a Sidak/Holmes post hoc test. Group comparisons will be made with an ANOVA/t-test for independent groups. If the test of normality should fail (Kolmogorov-Smirnov with Lilliefors correction), the corresponding non-parametric tests will be used, i.e. the Wilcoxon-Mann-Whitney Rank Sum Test for independent t-tests and ANOVA on rank for repeated measures (Tukey post hoc). Level for statistical significance will be set at the traditional $p \leq 0.05$. Effect sizes will be calculated according to Cohen (1988) with the help of an online effect size calculator (the CEM effect size calculator, Centre for Evaluation and Monitoring, Durham University, Durham, United Kingdom: <http://www.cemcentre.org/evidence-based-education/effect-size-calculator>). An effect size of ≥ 0.5 will be considered clinically relevant (two-sided). If there is a need for building indexes of different types of scores, Z-scores will be used. The statistical power of 0.8 can be reached with at least 10 subjects in two groups, based on previously published data on fitness development and depression score. Target recruitment is nonetheless set higher than this with $n = 30$ in each group.

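### The outcome called agility is static one-leg balancing time, and taking it from one attempt per eye condition at each visit probably costs precision

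*Protocol*

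**What the plan says.** All the relevant text is in Protocol section 4.1.

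- **Source and label.** The battery is introduced thus: "There will be strength and agility exercises as used by the KAN study". Its two components are push-ups and the Stork Balance Test.
- **What the balance test is.** "The balance test is a timed test where the goal is to keep one's balance as long as possible". The procedure is given a little later: "The Stork Balance Test involves keeping one's balance on one leg for as long as possible; once with open and once with closed eyes".
- **Which value is analysed.** "The change in the number of push-ups and the balancing time will be used for the strength/agility measures".
- **Why these tests.** "These tests are chosen because of ease of administration and the availability of such data for comparison".

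The same section requires post-tests to be carried out in the same way as the baseline tests, so the stated number of attempts applies at every visit. It sets 30 per group, significance at 0.05, and a two-sided standardised effect of 0.5 or more as clinically relevant. Its power statement rests on fitness development and depression score; balancing time is not mentioned there.

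**The concern.** **Construct.** Push-ups supply the strength half of the label, so agility rests on balancing time alone. The protocol's own description is of a person holding still. No test in the plan involves change of direction or speed of movement. If the label is carried into a report, an improvement in balancing time would appear under the name of something that was not measured.

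**Noise.** The score is the moment at which balance is lost, so one chance wobble can set the whole value. With one attempt at baseline and one at week 12, that error goes into the change twice. It does not favour either arm, but it shrinks the standardised effect and makes a null result harder to interpret. Section 4.1 doubts that many more than 60 to 80 participants will complete the trial, so reducing measurement error is one of the few ways left to gain precision on this outcome.

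**Working it through.** **1. Construct: the texts side by side.** The heading says strength and agility. The test description "The balance test is a timed test where the goal is to keep one's balance as long as possible" and the analysed value "The change in the number of push-ups and the balancing time will be used for the strength/agility measures" both concern balance. The described task and the label disagree, and the protocol's own terms for the test (balance test, balancing time) settle what is measured. No arithmetic is needed.

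**2. Number of attempts.** The phrase "once with open and once with closed eyes" is most naturally read as one attempt per condition. The section gives no practice trial, best-of rule, maximum time or choice of leg.

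**3. The plan's own power figure.** Section 4.1 states power 0.8 with at least 10 subjects in two groups but gives no effect size, so the figure cannot be reproduced. With 10 per group it implies d = 1.32 (two-sided t-test). It does not concern balancing time and says nothing about it either way.

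**4. Illustration for the outcome as defined, a change.**

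From the protocol: 30 per group; two-sided 0.05; standardised difference 0.5.

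Assumed, because the protocol gives no figure: single-attempt reliability *r* of 0.9, 0.7 or 0.5; true pre-post correlation ρ = 0.8; no dropout; independent errors across attempts and visits; approximately normal scores; the difference of 0.5 expressed in true-score SDs.

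With true-score variance 1 and the mean of *k* attempts:

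- error variance e = (1 − r) / (r·k)
- SD of change = √[2(1 + e − ρ)]
- effective d = 0.5 / SD of change
- power from the independent t-test

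| r | k | e | SD of change | effective d | power |
|---|---|---|---|---|---|
| 0.9 | 1 | 0.111 | 0.789 | 0.634 | 0.68 |
| 0.9 | 3 | 0.037 | 0.689 | 0.726 | 0.79 |
| 0.7 | 1 | 0.429 | 1.121 | 0.446 | 0.40 |
| 0.7 | 3 | 0.143 | 0.828 | 0.604 | 0.63 |
| 0.5 | 1 | 1.000 | 1.549 | 0.323 | 0.23 |
| 0.5 | 3 | 0.333 | 1.033 | 0.484 | 0.45 |

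With no measurement error (e = 0) the SD of change is √0.4 = 0.632, d = 0.791 and power is 0.85.

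**5. Sensitivity to the assumed correlation.** With ρ = 0.5 in the same formulas, the gains are smaller: 0.41 to 0.45 at r = 0.9, 0.29 to 0.39 at r = 0.7, and 0.20 to 0.31 at r = 0.5. The direction is the same in every cell; the size is not stable.

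**6. Week-12 scores only.** If the arms are compared on the later score alone, observed d = 0.5·√r, and the mean of three has reliability 3r/(1 + 2r). Power goes from 0.44 to 0.46 (r = 0.9), 0.36 to 0.43 (r = 0.7) and 0.27 to 0.38 (r = 0.5). Without any measurement error it is 0.48, so here the sample size is the larger limit.

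**The case against.** **The test is openly named.** The protocol calls it a balance test throughout, agility appears in neither the aim nor the objectives in section 3, and balancing time is not named as primary. This stands. It limits the labelling point to a minor correction, and it means one cannot say that a false agility claim will be made, only that the label invites one.

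**A reader might infer that one attempt is too noisy to show change with 30 per group.** The documents do not support that. They give no standard deviation, retest reliability or expected change for balancing time. On the week-12 comparison, single-attempt power runs from 0.23 (d = 0.5, reliability 0.4) to 0.95 (d = 1.0, reliability 0.9), so any verdict of this kind is decided by the assumption chosen. At d = 0.5 that comparison has only 0.48 power even with a perfect measurement, a limit that applies to every outcome compared in the same way.

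**The attempt count and scoring may be set by the survey procedure.** The tests are taken from the KAN study, whose procedure is not in the protocol. Practice trials or a scoring rule could be defined there. This is possible, but the protocol's own wording points to one attempt per condition and cites no other rule.

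**Comparability with the survey was a stated reason for the choice.** A mean of three attempts is not the same quantity as a single attempt. Keeping the first attempt as a separate value largely meets this, although whether that attempt matches the survey score cannot be checked from the document.

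**Skewed hold times may be log-transformed or analysed by ranks.** Section 4.1 provides for both. The power figures above are for a t-test on approximately normal scores, so they illustrate the effect of averaging and do not predict the result of the planned analysis.

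**Conclusion.** The point holds in two parts of unequal certainty. That the outcome labelled agility is static balancing time follows directly from the text. That a single attempt per eye condition costs precision is likely, because the error enters the change twice; the amount cannot be calculated from the protocol. Under the stated assumptions with ρ = 0.8, averaging three attempts adds between 0.11 (0.68 to 0.79) and 0.23 (0.40 to 0.63) to change-score power; with ρ = 0.5 it adds between about 0.04 and 0.12.

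This is a cheap improvement of minor severity. Balancing time is one of many outcomes, the quantity measured is disclosed, and the noise does not bias the comparison of arms. It does not follow that the trial cannot detect a change in balance.

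**What to change.** In Protocol section 4.1:

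1. Replace the single attempt by three attempts per eye condition, on the same leg at every visit, with a short rest between attempts. Define balancing time as the mean of the three. Record the first attempt as a separate value for comparison with the survey data.
2. Rename the outcome *strength and balance* wherever the text says strength and agility or strength/agility, and make no claim about agility.

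Cost: a few extra minutes at each physical test visit and a few changed sentences; no new equipment, staff or visits. The downside is some practice or fatigue across the three attempts, which should be similar in both arms.

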Drop-outs, either from the intervention or the control group, may cause problems for the study. If too many participants drop out and new participants cannot be recruited, the number might get too small for the results to be statistically relevant. The number of 60 participants makes this a particularly relevant issue here. Selection and mortality are chief concerns for any clinical trial, and a particular concern in samples of patients with mental illness and/or addiction. Thus, this study utilizes a prolonged recruitment period, also beyond the desired number of participants, and will offer minor incentives to participants (t-shirts, sports water bottles etc.). On the other hand, the study has to be feasible, and it would not be a realistic assessment of feasibility to presume that many more than 60-80 participants of the target group will complete the trial.

Mortality leads to the fact that the outcomes of the experiment are unknown for the participants who drop out. Reasons for drop-outs and proportions for each group will be reported. The drop-out event itself can give important information, especially in the event of many drop-outs. It might also be possible to compare those who drop out with those who continue, in terms of the outcome.

Group sessions give higher compliance, which in turn is important for the outcome for the participant, either improvement in physical fitness or substance use control (Richard A Brown et al., 2009; R. A. Brown et al., 2010; Donaghy & Mutrie, 1999; Read & Brown, 2003). The use of training contacts is therefore of interest as it increases the social element of the training.

In order to limit the number of drop-outs from the control group, the participants of this group will be given the opportunity to receive the intervention after three months. Thereby they will also get the chance to benefit from physical activity and to do what motivated them to participate in the project in the first place. Otherwise a resentful demoralization, they might develop once they realize that they are in the control group, could influence the psychosocial functioning and self-efficacy.

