Participants in the intervention group will start with the introductory meeting. The introductory meeting will enable the participants and training contact to get to know each other. Good personal chemistry is important, as they will spend much time together in the coming months. It is useful to note down interests, training ambitions and self-evaluated physical fitness level at this meeting, as this will help in the planning of the training. Training with a training contact is the primary intervention. Concerning the practical procedure, training contact and participant will meet for three hours a week⁶ (in either two or three sessions) for 12 weeks. The training contact will motivate and guide the participants. One goal is to enable the participants to conduct training alone by the end of the project. Training content can be chosen by the participant (to increase the likelihood of study completion) but should be feasible and consist of a combination of aerobic and muscle-strengthening activity. Training intensity should be increased gradually, to avoid injuries and create motivation. All training sessions will be recorded in a diary, where the type of exercise, time, intensity and other remarks are noted. Both the participant and training contact should make such recordings to make the documentation as complete as possible.

After the 12 weeks intervention period another testing will be conducted. This post-measurement will include the same tests as those performed at the baseline measurement.

Participants who were selected into the control group are on a waiting list for 12 weeks and receive treatment as usual. After three months they will go through the assessment procedure again. Subsequently, they will receive the same intervention as the original intervention group. They, too, will get a training contact for 12 weeks and will be tested afterwards.

As a follow-up, all participants will be assessed 12 months after baseline measurement. It is important that the post-measurement tests are carried out identically to those at pre-measurement, in order to obtain a valid result.

All sensitive data (digital and non-digital) generated is confidential and will be treated according to the standards set by the Norwegian Data Inspectorate (*Datatilsynet*) and in compliance with the Health Research Act and the Personal Data Act.

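### If the planned repeated-measures ANOVA covers all visits, it is a complete-case analysis: a missed 12-month visit removes a measured week-12 value from the over-time results

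*Protocol*

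**What the plan says.** Everything relevant stands in Protocol Section 4.1.

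- **Over-time analysis:** for results over time, "an ANOVA/t-test of repeated measures will be performed", followed by a Sidak/Holmes post hoc test. If the normality test fails, the over-time fallback is "ANOVA on rank for repeated measures (Tukey post hoc").
- **Between-group analysis:** "Group comparisons will be made with an ANOVA/t-test for independent groups", with a rank-sum test as fallback.
- **Visits:** after baseline, "After the 12 weeks intervention period another testing will be conducted" in the intervention arm, and controls are reassessed at three months. Controls then receive the intervention and have one further test. Finally, "As a follow-up, all participants will be assessed 12 months after baseline measurement". The aims for life satisfaction, executive function and distress are framed as change over 12 months.
- **Drop-out:** the section treats attrition as a main threat in this population and at this sample size. It states that "the outcomes of the experiment are unknown for the participants who drop out". It commits to reporting reasons and the proportion lost in each group. It adds, tentatively, that it may be possible to "compare those who drop out with those who continue, in terms of the outcome".

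The section does not say which visits enter the over-time ANOVA.

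**The concern.** Classical repeated-measures ANOVA and its rank version need a value at every visit in the model. A participant who attends baseline and week 12 but not month 12 is dropped entirely, so a valid 12-week change is lost. The method therefore discards most where the protocol itself expects most loss.

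Two things are at stake in the over-time results. The first is precision, because fewer 12-week changes are used than were measured. The second is who the results describe. Section 4.1 ties adherence to motivation, so people who stay a year are plausibly the more motivated ones, and their average change need not be that of everyone randomised. The direction of this bias is an inference from the protocol's own reasoning; it has not been computed.

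The drop-out paragraph adds a smaller difficulty. It calls the outcomes of drop-outs unknown and then suggests comparing drop-outs with completers on the outcome, without saying which observed values that comparison would use.

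**Working it through.** **Does the text point to an all-visits ANOVA?** A post hoc test over time is needed only with three or more time points. The schedule supplies three for everyone (baseline, week 12, month 12), and the stated horizon is 12 months. The only rank-based method named for repeated measures is an ANOVA on ranks; no paired two-visit rank test is named. The all-visits reading is therefore natural, though not stated outright.

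**Inputs.** Target sample: 60, with 30 per group (Section 4.1). Drop-out rates: the protocol gives none, so those below are assumptions. There is no figure of the plan's own on this point to reproduce.

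**Counts.** Let *a* be the share missing at week 12 and *b* the share missing at month 12.

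- Observed week-12 changes: 60 × (1 − a)
- Used by the all-visits ANOVA:
  - monotone drop-out (everyone missing at week 12 is also missing at month 12): 60 × (1 − b)
  - independent misses: 60 × (1 − a) × (1 − b)
  - misses that never overlap: 60 × (1 − a − b)

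| a / b | Observed | Used, monotone | Used, independent | Used, no overlap |
|---|---|---|---|---|
| 10% / 20% | 60 × 0.90 = 54 | 60 × 0.80 = 48 | 60 × 0.90 × 0.80 = 43.2 | 60 × 0.70 = 42 |
| 20% / 35% | 60 × 0.80 = 48 | 60 × 0.65 = 39 | 60 × 0.80 × 0.65 = 31.2 | 60 × 0.45 = 27 |

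**Standard error of the week-12 change.** If the standard deviation of the change is the same in those used and those observed, the ratio is √(observed / used).

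| a / b | Monotone | Independent | No overlap |
|---|---|---|---|
| 10% / 20% | √(54/48) = 1.06 | √(54/43.2) = 1.12 | √(54/42) = 1.13 |
| 20% / 35% | √(48/39) = 1.11 | √(48/31.2) = 1.24 | √(48/27) = 1.33 |

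The monotone column fits drop-out in the ordinary sense. The other two require some people to miss week 12 and come back at month 12.

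**A second view.** If everyone attends week 12 and 10% to 40% miss only month 12, the all-visits ANOVA discards 60 × 0.10 = 6 to 60 × 0.40 = 24 of 60 measured week-12 values.

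**The drop-out comparison.** Outcomes after drop-out do not exist, so a comparison on those cannot be made. What does exist is baseline for everyone tested, week-12 results for people lost between week 12 and month 12, and the fortnightly reports up to the time of loss. An all-visits ANOVA would leave out exactly those week-12 results.

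**The case against.** A reader might infer that a missed 12-month visit deletes week-12 data from the trial's analysis as a whole. The protocol does not support that. The independent-groups test at week 12, or its rank-sum fallback, uses everyone seen at week 12. That is also the only randomised contrast of trained with untrained patients, because controls are trained afterwards. The over-time wording also allows a t-test, and a paired test of baseline against week 12 needs no month-12 value. This objection stands, and it confines the point to the over-time ANOVA when run on all visits.

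A reader might also infer that the outcome comparison is the only planned check on drop-out and that it is impossible. Neither is right. Reporting reasons and group proportions is a firm commitment, whereas the comparison is only tentative. It can be made for people lost after week 12. What remains is wording that needs repair.

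It is tempting to add that controls lose more because they have a fourth test. That holds only if the extra test enters the model, which the protocol does not say; a joint two-arm ANOVA would naturally use the three common visits.

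Finally, missing-data handling commonly belongs in the SAP, which is not at hand, so its absence is no finding. But the protocol does name the method, and on its natural reading that method is complete-case. Prolonged recruitment, small incentives and delayed training for controls may limit the loss; they do not change how the analysis treats it.

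**Conclusion.** The point holds in limited form and is worth correcting. On the natural all-visits reading, the named over-time analysis discards measured week-12 values in a trial that expects drop-out, and its results describe only participants who completed the year. The randomised week-12 comparison is untouched.

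The loss of precision is modest under ordinary drop-out: a standard error 6% or 11% larger than necessary in the two scenarios. The 33% figure arises only with 20% and 35% missing and no overlap between the misses. All these sizes rest on assumed missing rates and on an equal standard deviation of change in those retained. The selection to year-long completers is the more serious consequence, but its size cannot be worked out from the protocol.

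**What to change.** Replace the repeated-measures ANOVA and its rank version by a linear mixed model for each outcome. Use the visits common to both arms (baseline, week 12, month 12), with visit as a category, an arm-by-visit term, one covariance structure fixed in advance and small-sample degrees of freedom. Every available measurement enters. Analyse the controls' additional post-training test separately, since the intervention arm has no matching visit.

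Reword the tentative comparison of drop-outs with completers so that it uses baseline values, and outcomes or fortnightly reports observed before drop-out, by arm. Do not choose model covariates by whether they turn out to predict drop-out; with about 60 people that would be data-driven selection.

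The cost is a change of wording and standard software, with no extra data collection. The downside is that the model relies on data being missing at random given what was observed. That cannot be verified, but it is a weaker assumption than complete-case ANOVA needs.
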